6.10. Previous and Concomitant Therapy

Previous medications are described in the originating studies.

Summaries of concomitant medications used for AD will be based on the mITT population.

At each visit, concomitant therapy will be recorded for each patient. Concomitant therapy for the treatment period is defined as therapy that starts before or during the treatment period and ends during the treatment period or is ongoing (has no end date or ends after the treatment period). Should there be insufficient data to make this comparison (eg, the concomitant therapy stop year is the same as the treatment start year, but the concomitant therapy stop month and day are missing), the medication will be considered as concomitant for the treatment period.

A summary of concomitant therapy including concomitant therapies of special interest will be provided for the mITT population.

6.11. Efficacy Analyses

The general methods used to summarize efficacy data, including the definition of baseline value for assessments are described in Section 6.2.

Efficacy analyses will generally be analyzed according to the groups in Table JAHN.6.3 and patients will be analyzed according to the IP being analyzed in the objective.

Table JAHN.6.3. Efficacy Analyses: Comparisons or Treatment Paradigms

Treatment Period	Treatment Groups: Originating Study Treatment to JAHN Treatment	Comparison or Treatment Paradigms	Analysis
Treatment Period 1 (main JAHN protocol)	Responders and Partial Responders: PBO to PBO (PBO), BARI 1 mg to BARI 1 mg (BARI 1 mg), BARI 2 mg to BARI 2 mg (BARI 2 mg), BARI 4 mg to BARI 4 mg (BARI 4 mg)	PBO, BARI 1 mg, BARI 2 mg, BARI 4 mg; descriptive	Primary, Secondary, Exploratory
	Nonresponders: PBO to BARI 2 mg, PBO to BARI 4 mg, BARI 1 mg to BARI 2 mg, BARI 1 mg to BARI 4 mg, BARI 2 mg to BARI 2 mg, BARI 2 mg to BARI 4 mg, BARI 4 mg to BARI 4 mg	PBO to BARI 4 mg vs PBO to BARI 2 mg; BARI 1 mg to BARI 4 mg vs BARI 1 mg to BARI 2 mg; BARI 2 mg to BARI 4 mg vs BARI 2 mg to BARI 2 mg	Secondary, Exploratory
Treatment Period 2 (Randomized Withdrawal and Downtitration SubStudy)	Treatment Groups: Bari 4 mg at Week 52 Bari 4 mg to Bari 2 mg Bari 4 mg to PBO Bari 2 mg at Week 52	Bari 4 mg to Bari 2 mg Bari 4 mg to PBO	Secondary

Treatment Period	Treatment Groups: Originating Study Treatment to JAHN Treatment	Comparison or Treatment Paradigms	Analysis
	Bari 2 mg to Bari 1 mg Bari 2 mg to PBO	Bari 2 mg to Bari 1 mg Bari 2 mg to PBO	
Treatment Period 2 (Non substudy) (main JAHN population)	Treatment Groups: Bari 4 mg Bari 2 mg Bari 1 mg PBO	No comparison	Secondary, Exploratory
Treatment Period 2 (Non substudy) (open label Bari 2mg population)	Treatment Groups: Bari 2mg	No comparison	Secondary, Exploratory

Abbreviations: BARI = baricitinib; PBO = placebo.

[Table JAHN.6.4](#) includes the descriptions and derivations of the primary, secondary, and exploratory efficacy outcomes.

[Table JAHN.6.5](#) provides the detailed analyses including analysis type, method and imputation, population, time point, and comparisons for efficacy analyses.

Table JAHN.6.4. Description and Derivation of Primary, Secondary, and Exploratory Efficacy Outcomes

Measure	Description	Variable	Derivation / Comment	Imputation Approach if Missing Components
Validated Investigator's Global Assessment for AD (IGA)	The validated IGA of the patient's overall severity of their AD, based on a static, numeric 5-point scale from 0 (clear) to 4 (severe). The score is based on an overall assessment of the degree of erythema, papulation/induration, oozing/crusting, and lichenification.	IGA score	Single item. Range: 0-4 0 represents "clear" 4 represents "severe"	Single item, missing if missing.
		
 ▪ IGA (0,1) ▪ IGA (0,1,2) 	
 ▪ Observed score of 0 or 1 ▪ Observed score of 0, 1, or 2 	Single item, missing if missing.
		Relapse	If IGA score at any visit after Week 52 is observed to be >2 then relapse = 'Y'	Missing if all post-Week 52 IGA assessments are missing
Eczema Area and Severity Index (EASI)	The EASI assesses objective physician estimates of 2 dimensions of atopic dermatitis – disease extent and clinical signs (Hanifin et al. 2001) – by scoring the extent of disease (percentage of skin affected: 0 = 0%; 1 = 1-9%; 2 = 10-29%; 3 = 30-49%; 4 = 50-69%; 5 = 70-89%; 6 = 90-100%) and the severity of 4 clinical signs (erythema, edema/papulation, excoriation, and lichenification) each on a scale of 0-3 (0 = none, absent; 1 = mild; 2 = moderate; 3 = severe) at 4 body sites (head and neck, trunk, upper limbs, and lower limbs). Half scores are allowed. Each body site will have a score that ranges from 0-72, and the final EASI score will be obtained by weight-averaging these 4 scores. Hence, the final EASI score will range from 0-72 for each time point.	EASI score	Derive EASI region score for each of head and neck, trunk, upper limbs, and lower limbs as follows: EASI _{region} = (Erythema + edema/papulation + Excoriation + Lichenification) * (value from percentage involvement), where erythema, edema/papulation, excoriation, and lichenification are evaluated on a scale of 0-3 and value from percentage involvement is on a scale of 0-6. Then total EASI score is as follows: EASI = 0.1*EASI _{head and neck} + 0.3*EASI _{trunk} + 0.2*EASI _{upper limbs} + 0.4*EASI _{lower limbs}	N/A – partial assessments cannot be saved
		
 ▪ Change from baseline in EASI score ▪ Percent change from baseline in EASI score 	Change from baseline: observed EASI score – baseline EASI score % change from baseline: $100 \times \frac{\text{Observed score} - \text{Baseline}}{\text{Baseline}}$	Missing if baseline or observed value is missing.
		EASI50	% Improvement in baseline ≥50%: % change from baseline ≤ -50	Missing if baseline or observed value is missing.
		EASI75	% Improvement in baseline ≥75%: % change from baseline ≤ -75	Missing if baseline or observed value is missing.

Measure	Description	Variable	Derivation / Comment	Imputation Approach if Missing Components
		EASI90	% Improvement in baseline $\geq 90\%$: % change from baseline ≤ -90	Missing if baseline or observed value is missing.
		Rebound	If EASI percentage change from originating study baseline at any visit after Week 52 is observed to be ≥ 125 , then disease rebound = 'Y'	Missing if baseline or observed value is missing.
Body Surface Area (BSA) Affected by AD	Body surface area affected by AD will be assessed for 4 separate body regions and is collected as part of the EASI assessment: head and neck, trunk (including genital region), upper extremities, and lower extremities (including the buttocks). Each body region will be assessed for disease extent ranging from 0%-100% involvement. The overall total percentage will be reported based off of all 4 body regions combined, after applying specific multipliers to the different body regions to account for the percent of the total BSA represented by each of the 4 regions.	BSA score	Use the percentage of skin affected for each region (0-100%) in EASI as follows: BSA = BSA _{head and neck} / 100/0.10 + BSA _{trunk} / 100 / 0.0333 + BSA _{upper limbs} / 100 / 0.05 + BSA _{lower limbs} / 100 / 0.025	N/A – partial assessments cannot be saved.
		Change from baseline in BSA score	Change from baseline: observed BSA score – baseline BSA score	Missing if baseline or observed value is missing.
SCORing Atopic Dermatitis (SCORAD)	The SCORing Atopic Dermatitis (SCORAD) index uses the rule of nines to assess disease extent (head and neck 9%; upper limbs 9% each; lower limbs 18% each; anterior trunk 18%; back 18%; and genitals 1%). It evaluates 6 clinical characteristics to determine disease severity: 1) erythema, 2) edema/papulation, 3) oozing/crusts, 4) excoriation, 5) lichenification, and 6) dryness on a scale of 0-3 (0=absence, 1=mild, 2=moderate, 3=severe). The SCORAD index also assesses subjective symptoms of pruritus and sleep loss in the last 72 hours on visual analogue scales (VAS) of 0-10 where 0 is no itch or sleep loss and 10 is worst-imaginable itch or sleep loss. These 3 aspects (extent of disease, disease severity, and subjective symptoms) combine to give a maximum possible score of 103 (Stalder et al. 1993; Kunz et al. 1997; Schram et al. 2012).	SCORAD score	SCORAD = A / 5 + 7B / 2 + C, where A is extent of disease, range 0-100 B is disease severity, range 0-18 C is subjective symptoms, range 0-20.	Missing if components A and B are missing or if component C is missing. Partial assessments performed by physician cannot be saved and partial assessments performed by subject cannot be saved.
		
 ▪ Change from baseline in SCORAD score ▪ Percent change from baseline in SCORAD score 	Change from baseline: observed SCORAD score – baseline SCORAD score % change from baseline: $100 \times \frac{\text{Observed score} - \text{Baseline}}{\text{Baseline}}$	Missing if baseline or observed value is missing.
		SCORAD75	% Improvement in baseline $\geq 75\%$: % change from baseline ≤ -75	Missing if baseline or observed value is missing.
		SCORAD90	% Improvement in baseline $\geq 90\%$: % change from baseline ≤ -90	Missing if baseline or observed value is missing.

Abbreviations: AD = atopic dermatitis; N/A = not applicable.

Table JAHN.6.5. Description of Primary, Secondary, and Exploratory Efficacy Analyses

Measure	Variable	Population ^a (Section 6.2.1)	Analysis Method ^b (Section 6.2.3)	Time Point	Analysis Type
Validated Investigator’s Global Assessment for AD (IGA) ^c	Proportion of patients with a response of IGA 0 or 1	mITT population from originating combination therapy study -responders, partial responders	Descriptive using NRI and mLOCF	Weeks 0-52	Primary for IGA (0,1) at Weeks 16, 36, and 52
	Proportion of patients with a response of IGA 0, 1, or 2	mITT population from originating combination therapy study -non responders	Logistic regression using NRI Descriptive using mLOCF	Weeks 0-52	Secondary for IGA (0,1,2) Primary for mLOCF Sensitivity for NRI
		mITT population from open-label study	Descriptive using NRI and mLOCF	Weeks 0-52	Exploratory
		mITT population per pooled Bari 2 mg-2 mg; Bari 4 mg-4 mg	Descriptive using NRI and mLOCF	Weeks 0-52	Exploratory
		Long-term Bari 4 mg population	Descriptive using Observed, NRI and mLOCF	Weeks 52-200	Exploratory
		Randomized Downtitration Withdrawal Substudy Population	Logistic regression using NRI and mLOCF	Week 52-200	Secondary for Week 68
		Randomized Downtitration Withdrawal Substudy Population with Week 52 IGA of 0 or 1			Exploratory for Other weeks Primary for mLOCF Sensitivity for NRI
		Period 2 non-substudy population Open-label Period 2 non-substudy population	Descriptive using observed, mLOCF and NRI	Week 52 to 200	Secondary, exploratory Primary for mLOCF Sensitivity for NRI
Time to retreatment (time to IGA ≥3)	Re-Treatment Substudy Population	Descriptive	Downtitration and withdrawal period	Secondary	

Measure	Variable	Population ^a (Section 6.2.1)	Analysis Method ^b (Section 6.2.3)	Time Point	Analysis Type
	Proportion of patients with IGA ≤2 within 16 weeks after retreatment	Re-Treatment Substudy Population	Descriptive	Week 52 to 200	Secondary
Eczema Area and Severity Index (EASI) ^c	Proportion of patients achieving EASI75 (achieving EASI percent change from baseline < -75) Proportion of patients achieving EASI50 Proportion of patients achieving EASI90	mITT population from originating combination therapy study -responders, partial responders	Descriptive using NRI and mLOCF	Weeks 0-52	Secondary for EASI75 Exploratory for EASI50 and EASI90 Secondary for mLOCF
		mITT population from originating combination therapy study -non responders	Logistic regression using NRI Descriptive using mLOCF	Weeks 0-52	Sensitivity for NRI
		mITT population from open-label study	Descriptive using NRI and mLOCF	Weeks 0-52	Exploratory
		mITT population per pooled Bari 2 mg-2 mg; Bari 4 mg-4 mg	Descriptive using NRI and mLOCF	Weeks 0-52	Exploratory
		Long term Baricitinib 4 mg population	Descriptive using Observed, NRI and mLOCF	Weeks 52-200	Exploratory
		Randomized Downtitration Withdrawal Substudy Population	Logistic regression using NRI and mLOCF	Week 52-200	Secondary for Week 68 Exploratory for Other weeks
		Randomized Downtitration Withdrawal Substudy Population with Week 52 IGA of 0 or 1			Secondary for mLOCF Sensitivity for NRI
		Period 2 non-study population Open-label Period 2 non-study population	Descriptive using observed, NRI and mLOCF	Week 52-200	Secondary, exploratory Secondary for mLOCF Sensitivity for NRI
Change from baseline in EASI score Percent change from baseline in EASI score	mITT population from originating combination therapy study -responders, partial responders	Descriptive using observed and mLOCF	Weeks 0-52	Exploratory Sensitivity for NRI	

Measure	Variable	Population ^a (Section 6.2.1)	Analysis Method ^b (Section 6.2.3)	Time Point	Analysis Type
		mITT population from originating combination therapy study -non responders	MMRM using observed Descriptive using mLOCF	Weeks 0-52	Exploratory Sensitivity for NRI
Eczema Area and Severity Index (EASI) ^c	Change from baseline in EASI score Percent change from baseline in EASI score	mITT population from open-label study	Descriptive using observed and mLOCF	Weeks 0-52	Exploratory
		Period 2 non-substudy population Open-label Period 2 non-substudy population	Descriptive using observed and mLOCF	Weeks 52-200	Exploratory
		Long term Baricitinib 4 mg population	Descriptive using observed and mLOCF	Weeks 52-200	Exploratory
		Randomized Downtitration Withdrawal Substudy Population Randomized Downtitration Withdrawal Substudy Population with Week 52 IGA of 0 or 1	ANCOVA using mLOCF	Week 52-200	Exploratory
Body Surface Area (BSA) Affected by AD	BSA Score Change from baseline in BSA Score	mITT population from originating combination therapy study - responders, partial responders	Descriptive using observed and mLOCF	Weeks 0-52	Exploratory
		mITT population from originating combination therapy study - nonresponders	MMRM using observed Descriptive using mLOCF	Weeks 0-52	Exploratory
		mITT population from open-label study	Descriptive using observed and MLOCF	Weeks 0-52	Exploratory
SCORing Atopic Dermatitis (SCORAD)	SCORAD score Change from baseline in SCORAD score Percent change from baseline in SCORAD score	mITT population from originating combination therapy study - responders, partial responders	Descriptive using observed and MLOCF	Weeks 0-52	Exploratory
		mITT population from originating combination therapy study - nonresponders	MMRM using observed Descriptive using mLOCF	Weeks 0-52	Exploratory
SCORing Atopic Dermatitis	Change from baseline in SCORAD score	mITT population from open-label study	Descriptive using observed and mLOCF	Weeks 0-52	Exploratory

Measure	Variable	Population ^a (Section 6.2.1)	Analysis Method ^b (Section 6.2.3)	Time Point	Analysis Type
(SCORAD) ^c	Percent change from baseline in SCORAD score	Period 2 non-substudy population Open-label Period 2 non-substudy population	Descriptive using observed and mLOCF	Weeks 52-200	Exploratory
	SCORAD score, Pruritus & Sleep Loss Percent change from baseline in SCORAD score, Pruritus & Sleep Loss	Long term Baricitinib 4 mg population	Descriptive using observed and mLOCF	Weeks 52-200	Exploratory
	Proportion of patients achieving SCORAD75 Proportion of patients achieving SCORAD90	mITT population from originating combination therapy study - responders, partial responders	Descriptive using NRI and mLOCF	Weeks 0-52	Exploratory
		mITT population from originating combination therapy study - nonresponders	Logistic regression using NRI Descriptive using mLOCF	Weeks 0-52	Exploratory
		mITT population from open-label study	Descriptive using NRI and mLOCF	Weeks 0-52	Exploratory
		Period 2 non-substudy population Open-label Period 2 non-substudy population	Descriptive using observed, NRI and mLOCF	Weeks 52-200	Exploratory
		Long term Baricitinib 4 mg population	Descriptive using NRI, observed and mLOCF	Weeks 52-200	Exploratory

Abbreviations: AD = atopic dermatitis; ANCOVA = analysis of covariance; Bari = baricitinib; DBL = database lock; EE = efficacy evaluable; Feb = February; mITT = modified intent-to-treat; mLOCF = modified last observation carried forward; MMRM = mixed-model repeated measures; NRI = nonresponder imputation.

- ^a Populations from originating studies for reporting periods of Weeks 0-52 are on the mITT population; they are reported by responder status from originating study: responders, partial responders, responders + partial responders and nonresponders. Populations for visit-wise analyses for those who entered the randomized withdrawal and downtitration study are based on efficacy evaluable sets for each of Week 56, 60, 64, and 68 (defined in Section 6.2.1).
- ^b All categorical endpoints use NRI, unless otherwise stated.
- ^c Descriptive using observed data for the endpoints beyond Week 104, unless otherwise stated.

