**Type of Patient and Disease Characteristics**

- [3] have a diagnosis of AD at least 12 months prior to screening, as defined by the American Academy of Dermatology: Guidelines of care for the management of AD; Section 1. Diagnosis and assessment of atopic dermatitis (see [Attachment 3](#)).
- [4] have moderate to severe AD, including all of the following:
- Eczema Area and Severity Index (EASI) score  $\geq 16$  at screening (Visit 0) and at enrollment (Visit 1)
  - IGA score of  $\geq 3$  at screening (Visit 0) and at enrollment (Visit 1)
  - $\geq 10\%$  of body surface area involvement at screening (Visit 0) and at enrollment (Visit 1).
- [5] have a documented history by a physician and/or investigator of inadequate response to existing topical medications within 6 months preceding screening, or history of intolerance to topical therapy as defined by at least 1 of the following:
- inability to achieve good disease control defined as mild disease or better (e.g., IGA  $\leq 2$ ) after use of at least a medium potency TCS for at least 4 weeks, or for the maximum duration recommended by the product prescribing information (e.g., 14 days for super-potent TCS), whichever is shorter. Topical corticosteroids may be used with or without topical calcineurin inhibitors.
  - Patients who failed systemic therapies intended to treat AD within 6 months preceding screening, such as cyclosporine, methotrexate, azathioprine, and mycophenolate mofetil will also be considered as a surrogate for having inadequate response to topical therapy.
  - documented history of clinically significant adverse reactions with the use of TCS such as skin atrophy, allergic reactions, systemic effects that in the opinion of the investigator outweigh the benefits of retreatment.
- [6] agree to discontinue use of the following excluded medications/treatments for at least 4 weeks prior to enrollment (Visit 1) and throughout the study:
- oral systemic corticosteroids
  - systemic immunomodulators, including, but not limited to, cyclosporine, methotrexate, mycophenolate mofetil, and azathioprine
  - any other systemic therapy used to treat AD or symptoms of AD (approved or off-label use)
  - phototherapy, includes therapeutic phototherapy (psoralen plus ultraviolet-A, ultraviolet-B), excimer laser as well as self-treatment with tanning beds.

- [7] agree to discontinue use of the following excluded medications for at least 2 weeks prior to enrollment (Visit 1) and throughout the study:

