- *Section 6.3* – added week 52 baseline values for Period 2 covariate adjustments.
- *Section 6.4* – the following changes were incorporated:
 - added retreatment after downtitration or early withdrawal as an intercurrent event
 - added Period 2 censoring rule
 - deleted section on mBOCF method for missing data
- *Table JAHN.6.2* was updated as follows:
 - deleted placebo multiple imputation (pmi) method for missing data handling for IGA 0,1 endpoint
 - modified last observation carried forward (mLOCF) added as an imputation method
 - deleted mBOCF imputation method
 - added imputation methods used in Period 2
- *Section 6.7* – added patient disposition calculation for Period 2
- *Section 6.8* – added patient compliance calculation for Period 2
- *Section 6.9.1* – added background therapy calculation for Period 2
- *Section 6.7* – added patient disposition calculation for Period 2
- *Table JAHN.6.3* – added treatment groups for Period 2
- *Table JAHN.6.4* – added variables relapse and rebound
- *Table JAHN.6.5* – added analysis for the following:
 - patients originating from combination therapy study
 - patients entering Period 2
 - changed time point analyzed for monotherapy studies in accordance with the US DBL

- added analysis for endpoints rebound and relapse
- *Tables JAHN.6.7* – added analysis corresponding to patients originating from combination therapy study
- *Section 6.8* – added safety analysis for patients entering Period 2
- *Appendix 1* – aligned with protocol amendment JAHN(7.1)
- *Section APP.1.2.5; Table APP.1.3 and APP.1.4* – clarified that for the EU and Japan DBLs the efficacy and health outcome analyses will include descriptive statistics for Weeks 0 through 36 only
- *Figure APP.1.2* – changed to reflect the change in Study Period 2 timeline.
- *Section APP.1.2.8* clarified that the by-patient listing for treatment assignments will be provided for the ITT population
- *Section APP.1.2.3.2.1* – defined Week 24 efficacy evaluable set for open label patients
- *Table APP.1.3* – changed analysis time period to be Week 0 to 16 and Week 24
- *Table APP.1.4* – added analysis for the following endpoints:
 - 4-point improvement in Skin Pain NRS
 - 1.5-point improvement in ADSS Item 2 score
 - 4-point improvement in POEM score
 - DLQI (0,1) response
 - 4-point improvement in DLQI score

SAP Version 5 was approved 19 May 2020 prior to the 4-month safety update (20 May 2020). The overall changes incorporated in Version 5 are as follows:

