- **Screening and baseline period:** Screening should occur during the last visit of the originating study unless the patient received oral systemic AD treatment as rescue therapy during the originating study and needs additional time to complete the required 4-week washout period or the sponsor gave approval.
- **Treatment Period 1:** Treatment period from Week 0 to Week 52. Patients will be classified as responders, partial responders or nonresponders at the entry of Study JAHN based on the criteria given in Section 5.1.

- Treatment Period 2: Treatment period from Week 52 to 200 and will contain a randomized withdrawal and downtitration substudy. At Week 52, all patients will be evaluated for substudy eligibility, and the criteria are given in the Protocol. Patients not entered in the substudy will continue on their current treatment.
- Posttreatment follow-up period: Period from Week 200 (Visit 22) or Early Termination Visit (ETV) to approximately 28 days after the last dose of IP.

Abbreviations: BARI = baricitinib; IGA = Investigator’s Global Assessment; TCS = topical corticosteroids.

a Background TCS may be initiated or reinitiated at any time during the study, following the guidelines in the Protocol (Section 7.7.1) and will be provided as part of rescue or retreatment any time a patient’s IGA score becomes ≥ 3 as described in the Protocol (Sections 5.1.2.1 and 5.1.3.1).

b Eligible patients will be rerandomized in the withdrawal and downtitration substudy as described in the Protocol (Section 5.1.3.1). Patients who do not enroll in the substudy will remain on their treatment.

c Patients enrolled in the substudy will automatically be retreated if their IGA score becomes ≥ 3 as described in the Protocol (Section 5.1.3.1).

d Rescue is available as described in the Protocol (Section 5.1.2.1).

Figure JAHN.5.1. Illustration of study design for Clinical Protocol I4V-MC-JAHN.

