 - If year of onset is missing, duration of AD will be set as missing. Otherwise, unknown month will be taken as January, and unknown day will be taken as 01. The duration of AD will be rounded to 1 decimal place.
- duration of AD (years) category (0 to <2 years, 2 to <5 years, 5 to <10 years, 10 to <20 years, ≥20 years)
- diagnosis age (year), derived using diagnosis date as the reference start date and July 1st of birth year and truncated to a whole-integer age
- diagnosis age group (<18, ≥18 to <50, ≥50 years old)
- change from baseline = postbaseline measurement at Visit x – baseline measurement from originating study
 - If a baseline value is missing, it will not be imputed and the change from baseline will not be calculated.
- percent change from baseline at Visit x:

$$([\text{postbaseline measurement at Visit x} - \text{baseline measurement}] / \text{baseline measurement}) * 100$$
 - If a baseline value is missing, it will not be imputed and percent change from baseline will not be calculated.
- Weight (kg) = weight (lbs) * 0.454
- Weight category (<60 kg, ≥60 to <100 kg, ≥100 kg)
- Height (cm) = height (in) * 2.54
- cyclosporine inadequate efficacy prior to entry into originating study (yes, no)
 - Set to **yes** if the reason for discontinuation is inadequate response.

- cyclosporine intolerance prior to entry into originating study (yes, no)
 - Set to **yes** if the reasons for discontinuation are: intolerance to medication or contraindication (physician indicated cyclosporine was used and a contraindication was noted).
- cyclosporine contraindication (ineligible) prior to entry into originating study (yes, no)
 - Set to **yes** if cyclosporine was never used because of a contraindication.
- cyclosporine inadvisable prior to entry into originating study (yes, no)
 - Set to **yes** if the following reasons were selected for either not using the medication or discontinuing the medication:
 - reason for not using medication: physician decision, concern about side effects, unfavorable benefit risk, contraindication.
 - reasons for discontinuation: inadequate response, intolerance to medication, or contraindication.
- TCNI inadequate efficacy prior to entry into originating study (yes, no)
 - Set to **yes** if the reason for discontinuation is inadequate response.
- TCNI intolerance prior to entry into originating study (yes, no)

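### Rebound is defined as an EASI percent change of at least 125, which means 2.25 times baseline; EASI stops at 72, so no patient with a baseline above 32 can meet it

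*SAP*

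**What the plan says.** The EASI block of SAP Table JAHN.6.4 (Section 6.11) contains a rebound variable: "If EASI percentage change from originating study baseline at any visit after Week 52 is observed to be" at least 125, rebound is set to yes. Four other statements fix what that means.

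- **Scale.** Section 6.2.4 ("percent change from baseline at Visit x") and the EASI rows of Table JAHN.6.4 both define percent change as observed minus baseline, divided by baseline, times 100.
- **Sign.** Improvement is negative. Table JAHN.6.5 describes EASI75 as "achieving EASI percent change from baseline < -75", and the EASI50, EASI75 and EASI90 rows beside rebound in Table JAHN.6.4 use negative cut-offs. A value of +125 is therefore a worsening.
- **Ceiling.** "Each body site will have a score that ranges from 0-72", and the total is a weighted average of the four sites: "Hence, the final EASI score will range from 0-72 for each time point".
- **Baseline.** The rebound row names the originating-study baseline. Section 6.2.2 also uses that baseline for EASI percent change in Period 2, rather than Week 52.

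Protocol inclusion criterion [4] requires an "Eczema Area and Severity Index (EASI) score" of at least 16 at screening and at enrolment. Protocol Section 4.5 says the feeder studies used the same entry criteria.

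The current Table JAHN.6.5, which lists the planned efficacy analyses, has no rebound row. The one reference to analysing it is the Version 4 entry in SAP Section 3 ("added analysis for endpoints rebound and relapse"), which describes an older text.

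**The concern.** Rebound is the only variable in the plan that counts individual patients whose disease becomes substantially worse than it was before treatment. That question arises naturally in a withdrawal and downtitration substudy.

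A threshold set as a large relative increase on a bounded scale fails from the top down. The more severe the disease before treatment, the less room is left to register a worsening, and beyond some baseline the answer is no by construction. Those patients would still sit in the denominator and dilute the rate. A reader given a rebound percentage from this rule would have no means of telling a true absence of rebound from a threshold that could not be reached.

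**Working it through.** **Inputs.** Rebound cut-off: +125 (Table JAHN.6.4). Percent change: 100 × (observed − baseline)/baseline (Section 6.2.4, Table JAHN.6.4). EASI construction and range: Table JAHN.6.4. Lowest eligible baseline: 16 (inclusion criterion [4]).

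**Step 1: reproduce the SAP's maximum.** Each body site scores up to (4 signs × 3) × 6 = 72. The weights are 0.1 + 0.3 + 0.2 + 0.4 = 1, so the largest total is 72, as stated.

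**Step 2: turn the cut-off into a multiple of baseline.** 100 × (observed − baseline)/baseline ≥ 125 gives observed ≥ (1 + 1.25) × baseline = 2.25 × baseline.

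**Step 3: find the highest baseline that can qualify.** 72/2.25 = 32. A patient at exactly 32 qualifies only at the maximum score. Half scores are allowed, and the next attainable total is 32.05, which would need 72.11. A listing of all attainable totals found none above 32 that can reach +125.

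**Step 4: compare the rule as written with the alternative reading (125% of baseline, a percent change of 25 or more).**

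| Baseline EASI | Largest possible percent change | EASI needed at +125 | EASI needed at +25 |
|---|---|---|---|
| 16 | 350.0 | 36 | 20 |
| 20 | 260.0 | 45 | 25 |
| 25 | 188.0 | 56.25 | 31.25 |
| 30 | 140.0 | 67.5 | 37.5 |
| 32 | 125.0 | 72 | 40 |
| 33 | 118.2 | 74.25 (impossible) | 41.25 |
| 40 | 80.0 | 90 (impossible) | 50 |

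Under the alternative reading the limit would be 72/1.25 = 57.6.

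**Step 5: look for anything that changes the result.** The documents contain no second definition of rebound, no other scale and no exception for high baselines. A Week 52 baseline would lower the bar for patients whose EASI had fallen on treatment, but the rebound row names the originating-study baseline. Addendum patients have no originating study. Section 6.2.2 gives directly enrolled patients their JAHN baseline for efficacy, and the limit of 32 is the same for them.

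**The case against.** The strongest reply concerns consequence. Rebound is not among the SAP's stated objectives, and it has no row in Table JAHN.6.5, no place in the retreatment summaries of Section 6.11.2 and no entry in the Appendix 2 substudy list. No primary, secondary or listed exploratory result depends on it. Loss of control is covered by the relapse variable (IGA above 2) and by time to retreatment, a secondary endpoint. EASI change and percent change are analysed by ANCOVA in the substudy, so average worsening beyond pre-treatment levels would show. All of this stands and limits the severity. It does not repair the derivation, which is still in the current SAP, and a mean does not replace a count of patients.

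Three stronger readings are tempting and should be resisted.

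- **That the trial would report no rebound whatever happened.** Baselines from 16 to 32 can qualify.
- **That retreatment puts the threshold out of reach for everyone else.** The SAP says "Patients enrolled in the substudy will automatically be retreated if their IGA score becomes" 3 or more, and Section 6.4 censors efficacy data after retreatment. However, IGA and EASI are recorded at the same visits, so the EASI at the visit that triggers retreatment should still count. Visits between Weeks 52 and 104 are 4 to 12 weeks apart, which leaves time for a flare. The documents give no data on how high EASI is at that point, and the same censoring would apply to any other cut-off.
- **That the sponsor meant 125% of baseline.** This is plausible, but no passage says so.

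**Conclusion.** The point holds for the rule as written, and the size of the limit is exact: 2.25 times baseline, impossible above 32. It rests only on the SAP's own percent-change formula and its EASI ceiling. A low rebound count under this rule would be partly an artefact of the scale.

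How many patients are affected is unknown. Of the eligible baseline range 16 to 72, the part above 32 is 40/56 = 71% of the scale width. A reader might take this for a share of patients, but it is not one: the documents give no baseline EASI distribution. Substudy patients are also selected on IGA 0 to 2 at Week 52, so their baselines may differ from those of all enrolled patients.

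This should be fixed, but it does not threaten the trial's main conclusions. The variable is outside the stated objectives and has no planned analysis in the current SAP.

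**What to change.** 1. State the intended threshold on one unambiguous scale. If 125% of baseline was meant, define rebound as observed EASI of at least 125% of baseline, that is, a percent change of at least 25; only baselines above 57.6 are then out of reach. If +125 was meant, say that patients with baseline EASI above 32 cannot meet it, and report rebound with that denominator limitation.
2. Align the row with Section 6.2.2 by naming the JAHN baseline for open-label addendum patients.
3. Add a descriptive rebound row by rerandomized arm to Table JAHN.6.5, or delete the derivation.

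The work is a few lines of SAP text and one programming threshold, and rebound can be re-derived from stored scores. The real cost is timing. The Version 8 entry in SAP Section 3 states that data to Week 104 are already locked, so the change must be labelled a post hoc correction. If the threshold falls to 25, the reported rebound rate may rise.
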